Project title: Utilizing telemedicine for delivery of postoperative care following minimally-invasive gynecologic surgery: A randomized controlled trial

Principal Investigator: [name] MD FACOG

Co-Investigators: [name] MD

Research Associate: [name]

Biostatistician: [name]., Professor

Affiliations: Texas Tech University Health Science Center El Paso, Paul L. Foster School of Medicine

Background:

The wide-spread use of minimally invasive techniques in gynecologic surgery has brought several tangible benefits to patients including faster-recovery times, shorter hospital stays, decreased risk of long term complications, to name a few.¹⁻³ Technological advances such as the development of robotic assistance have allowed to further expand the number of cases that can be performed via a minimally invasive approach.⁴ The shift has been such that the landscape regarding operative routes in gynecologic surgery has completely reversed, with now the majority of cases being performed laparoscopically.⁵ Although much has changed intraoperatively, the surrounding structure of an operative has lagged. Specifically, preoperative and post-operative visits are still conducted in a similar way than how it was done 20 years ago. Despite leaps in technology, the field of gynecologic surgery has been slow to widely implement these advances into perioperative practice. One of the specific areas of opportunity is the postoperative visit. It is common practice in the majority of fields to have a visit with the patient approximately 2 weeks after surgery. The objective of this visit is to evaluate how the patient has been progressing, examine the wound site(s), and discuss pathology results from any specimens that were removed during the procedure.

The logistics of this visit involve blocking a time-slot in an established clinic day. Patient is required to transport herself to the clinic site. Once checked-in, there may be a waiting period before being placed in a room for the practitioner to conduct the visit. Once the visit is started, as long as there are no issues, the duration of the interaction may range on average between 3-7 minutes.

Despite these visits being short and usually straight-forward, the invested time that patients have to dedicate is substantially greater than the actual interaction with the clinician. Furthermore, because of the advantages of minimally invasive surgery, many patients have already returned to work by the time of the postoperative visit which may result in a disruption of their daily work schedule.

The ubiquitousness of high-speed internet and mobile phones have allowed for the field of tele-medicine to thrive in recent years.^{6,7} Although wide-spread application of this modality has not been implemented in the field of gynecologic surgery, other areas such as urology and pediatrics have successfully implemented tele-medicine programs, specifically for postoperative patients, yielding promising results.^{8,9}

We propose a pilot project in which enrolled patients undergoing major gynecologic surgery will be randomized to either a traditional office postoperative visit or a telemedicine postoperative visit. The two groups will then be compared on a variety of metrics including clinical outcomes, patient satisfaction and time.

Objectives

1. Determine if there are differences in patient satisfaction between traditional postoperative visits and telemedicine postoperative visits
2. Determine the difference in time invested from the patient's side and clinicians side in order to complete the postoperative visit interaction
3. Analyze if there is a difference between groups regarding visits to the emergency department related to the surgery, delayed postoperative complications, etc.

Hypothesis

Patient satisfaction will be greater in the tele-medicine group.

Total time invested will be decreased.

There will be no difference in visits to the emergency department or unrecognized postoperative complications

Inclusion criteria

Female patients between ages 18-60

Have access to smart-phone with video /audio and internet capabilities

Undergoing laparoscopic gynecologic surgery that requires a postoperative visit

- Total laparoscopic hysterectomy
- Laparoscopic removal of adnexal structures
- Laparoscopic excision of endometriosis

Exclusion criteria

Patient unwilling to participate

Patient unwilling to install and utilize the telemedicine app on their smart phone.

Recruited participants will be deemed ineligible to continue the study if:

- After recruitment, participant experiences surgical complications (bladder or bowel injury, etc) that require face-to-face postoperative care
- After recruitment, participant visits the emergency room (ER) for postoperative complaints between surgery and scheduled postoperative visit

Materials and Methods

Study design: Randomized controlled trial.

Once IRB approval is obtained, we will begin recruitment based on the stated inclusion and exclusion criteria. Invitation to participate will be extended to eligible patients by clinic staff with a direct care relationship to the patient during their pre-operative visit in the TTUHSC El Paso Ob-Gyn department. If the patient agrees to participate, research staff will be called in to explain the study in more detail. The patients will be advised that if they agree to enroll, there is a 50% chance their post-operative visit may be via tele-medicine and 50% chance it will be as a traditional visit in the office. They will be asked to fill out a short survey that verifies they have a compatible mobile phone, and will be asked to download the appropriate app. An instruction sheet on how to utilize the tele-medicine application will be given to all patients, to be used in case they are allocated to the tele-medicine group. Once enrolled, surgery will proceed as planned. After surgical stop-time, patients will be allocated to either a traditional postoperative visit group or a tele-medicine postoperative visit via block-randomization, utilizing block sizes of 4:6. This will be achieved by giving patients a sealed envelope that allocates them in a sequential fashion based on a previously generated random series. The envelope will contain information regarding group assignment, along with simple instructions as to how to schedule the post-operative visit within a window between one and three weeks from the surgery.

Both the tele-medicine and traditional visits will be carried out using the same structure.

- 1) Inquire about any concerns the patient has regarding recovery.
- 2) Review findings and procedures done during surgery and pathology results.
- 3) Visually examine abdominal laparoscopic port-sites.
- 4) The opportunity for the patient to ask any additional questions.

In the case of the telemedicine visits, they will open by asking the patient to state her full name, and her date of birth. Additionally, this will be correlated with the code in the instruction sheet in order to verify identity.

A video-call application that is HIPAA compliant and easily accessible from mobile phones or video-enabled PCs will be used (doxy.me). A Business Associate Agreement between TTUHSC and Doxy.me has been generated in order to comply with HIPAA requirements. Patients will be given a time when they will receive their virtual appointment link, which will be sent to their mobile phone via text. It is expected that patients will use their phone to establish the connection. Providers will utilize a computer station set up with a camera and audio equipment, with a professional appearing backdrop. As part of the consent form, patients will be made aware that they may incur in data charges if they are using a limited data plan, and they are responsible for this expense.

Data will be collected in a de-identified manner. Baseline variables that will be captured include age, ethnicity, BMI, parity, distance from home address to the clinic in miles (calculated using Google maps). Surgery performed and operating time will also be collected. Post-operative visits will be timed. In the case of telemedicine, recorded time will be from when connection is established until disconnection. In the case of the traditional visit, it will be time from when the provider enters the exam room until time the patient exits). Patients will be contacted by phone between 7 to 14 days after the postoperative visit and they will be subjected to a PSQ-18 (Patient satisfaction questionnaire) focused on their post-operative visit, which will be conducted by a member of the research staff blinded to allocation. We will also inspect their medical records to determine if there were any phone calls to the clinic/call-center or visits to the emergency department following the postoperative encounter (within the first 30 days after surgery). In addition to the PSQ-18 questions (after they are completed), patient's will be asked "If they had the opportunity to have switched groups, would they?" and then they will be asked to give an estimate of how much time they utilized in order to complete the postoperative visit including transportation, waiting time, etc. (rounded to the nearest 15 minute increment).

Sample size:

Our primary outcome is to detect a difference in patient satisfaction. If we expect a 20% relative increase in the experimental arm, assuming two-tailed testing with an alpha of 0.05, and power of 80%, we will need a total sample size of 64 patients. This is considering a base satisfaction score of 70, with a standard deviation of 20.

Safety Procedures:

-Confidentiality and Privacy: Data will be stored in a secure de-identified database. No personal/identifiable information will be collected in this database. A separate list that contains a list of enrolled patients, with information including patient name, phone number and internal research code will also be generated for the purpose of performing the follow-up surveys. The information from the surveys will then be uploaded into the de-identified database by using the internal research code.-Safety – A member of the research staff will be assigned as a safety monitor. Interval analysis will be performed for every 20 patients recruited. If the experimental arm demonstrates an increase of greater than 10% in visits to the emergency-room related to post-operative complaints, or an increase in unexpected complications (wound infection, wound dehiscence, etc.), the study will be halted. However, only patient's undergoing minimally invasive surgery will be included, which is known to have a lower wound-related complication rate than traditional surgery, so we do not expect any significant difference regarding complications.

Data Management:

All data will be collected in a de-identified fashion and stored on Redcap, which is approved TTUHSC IT software. Only approved members of the research team will be granted access. The data will be stored in a secured server. Data will not be linked by code to any identifying information.

Data analysis:

All data analysis will be carried out in SPSS version 24 (IBM, Armonk, NY, USA). We will use T-student to compare demographic variables that are continuous (age, BMI), as well as duration of the visit and number of readmissions or phone-calls. Pearson's Chi Square will be used when analyzing categorical binary variables.

Strengths/limitations

This is an innovative study that seeks to apply existing and well established technology to improve patient experience in regards to the postoperative portion of their care. If found to be effective, it could also have the potential of reducing costs for the patient and clinic. The study is strong given its randomized nature. Randomization will occur after the surgical procedure is completed to avoid bias that could affect intra-operative technique or decisions. We will also use validated instruments to assess patient satisfaction.

The main limitation of the study is that patients and providers who are doing the post-operative visit cannot be blinded. This may lead to some degree of subconscious bias in the way the visits (traditional or tele-medicine) are carried out, which could potentially impact duration and patient satisfaction. We will attempt to mitigate this by utilizing a standardized visit structure which is exemplified in the methods section. Additionally, the research staff that will conduct the survey will be blinded to allocation. Patients will be instructed during the consenting process to avoid revealing their group when the surveyor calls.

Timeline

Accrual will commence after IRB approval. We expect to enroll on average 4 patients per week.

References

2. ACOG Committee Opinion No. 444: choosing the route of hysterectomy for benign disease. *Obstet Gynecol*. 2009;114(5):1156-1158.
7. Gutierrez G. Medicare, the Internet, and the future of telemedicine. *Crit Care Med*. 2001;29(8 Suppl):N144-150.

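### The no-difference hypothesis for emergency visits and complications has only tests of difference behind it, and 64 patients are too few for a non-significant result to support it

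*Combined protocol and SAP*

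**What the plan says.** The Hypothesis section predicts that "There will be no difference in visits to the emergency department or unrecognized postoperative complications". The matching item under Objectives is neutral: "Analyze if there is a difference between groups regarding visits to the emergency department related to the surgery".

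The Data analysis section names two methods. The t-test is for continuous demographics, "as well as duration of the visit and number of readmissions or phone-calls". For the rest, Pearson's "Chi Square will be used when analyzing categorical binary variables". Neither emergency visits nor complications are named. If each is scored yes/no per patient, chi-square applies by inference.

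The Sample size section derives the total from satisfaction alone: "we will need a total sample size of 64 patients". The only figure attached to emergency visits is the halting trigger under Safety Procedures, an "increase of greater than 10% in visits to the emergency-room". Its scale, absolute or relative, is not stated.

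Materials and Methods has the record review count "visits to the emergency department following the postoperative encounter (within the first 30 days after surgery"), with the visit scheduled one to three weeks after surgery. The eligibility section makes a patient ineligible to continue if she goes to the emergency room for postoperative complaints before that visit.

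**The concern.** A test of difference cannot establish that there is none. To support the third hypothesis, the plan would need a largest acceptable difference and an interval that excludes anything worse. Failing that, it should present the comparison as estimation. It does neither. The Safety Procedures section already words its expectation for complications as the absence of a significant difference, so a p-value above 0.05 could easily be reported as confirming the hypothesis.

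Readers will want to know whether replacing an office visit with a video call leads to more emergency visits or missed complications. With few events and 32 patients per arm, a non-significant result is likely whether or not that happens.

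**Working it through.** **1. The plan's own figure.** Inputs from the Sample size section: base 70, relative increase 20% (0.20 × 70 = 14 points), SD 20, two-sided alpha 0.05, power 80%.

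n per arm = 2 × (1.960 + 0.842)² × 20² / 14² = 2 × 7.85 × 400 / 196 ≈ 32.0

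Rounded up this is 33 per arm (66 in total). At 32 per arm the normal-approximation power is 79.96%. The 64 is therefore reproduced, for satisfaction only. Allocation is 1:1, so 32 per arm is used below.

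**2. Time in which emergency visits are counted.** Counting starts after the visit (day 7 to 21) and stops at day 30, which leaves 30 − 21 = 9 to 30 − 7 = 23 days per patient. Patients with an earlier emergency visit do not continue. Both features reduce the number of events.

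**3. Power of the inferred chi-square test.** Rates are assumed. All 33 × 33 possible outcomes at 32 per arm were enumerated, and the binomial probabilities of those with uncorrected p < 0.05 were summed.

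| Control v telemedicine | Power | Chance of missing the rise |
|---|---|---|
| 2% v 12% | 35% | 65% |
| 5% v 15% | 28% | 72% |
| 10% v 20% | 20% | 80% |

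Fisher's exact test would bring power down to about 11% in all three cases.

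**4. An example.** With 5 events v 1:

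χ² = 64 × (5 × 31 − 1 × 27)² / (32 × 32 × 6 × 58) = 2.94, p = 0.086

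The observed difference is (5 − 1)/32 = 12.5 points, yet the test is non-significant. A 4 v 0 split gives p = 0.039.

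**5. What an interval could exclude.** As a yardstick only, take the 10% trigger as 10 absolute points. The Newcombe upper limit for the difference p₁ − p₂ is

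(p₁ − p₂) + √[(u₁ − p₁)² + (p₂ − l₂)²]

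where l and u are Wilson limits. At 0 v 0 this reduces to z²/(n + z²) = 3.84 / 35.84 = 0.107. At 1 v 1 the Wilson limits for 1/32 are 0.0055 and 0.1574, so the upper limit is √(0.1262² + 0.0258²) = 0.129.

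| Events | Two-sided 95% upper limit | One-sided 95% upper limit |
|---|---|---|
| 0 v 0 | 10.7 points | 7.8 points |
| 1 v 1 | 12.9 points | 10.0 points |
| 2 v 2 | 14.6 points | 11.7 points |

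**6. How often 10 points would be excluded when true rates are equal** (same enumeration, 32 per arm).

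| True rate, both arms | Two-sided 95% | One-sided 95% |
|---|---|---|
| 1% | 20% | 73% |
| 2% | 26% | 57% |
| 5% | 25% | 41% |
| 10% | 22% | 34% |

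**7. Size needed.** The smallest n per arm giving at least an 80% chance of a two-sided upper limit below 10 points is 59 (true rate 2%), 93 (5%) or 148 (10%).

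**The case against.** The best defence is that the error is anticipated rather than written down. Nowhere does the protocol say a non-significant result will be taken as equivalence. The hypothesis can be read as a prediction, and a test of difference suits the neutral objective. The study calls itself a pilot, satisfaction is primary, and low power for rare secondary events is to be expected. The interim safety comparison, every 20 patients, also means that emergency visits do not rest on one p-value.

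The point about status stands and keeps this from being a major fault. The rest does not remove the problem. A halting trigger says when to stop, not when to conclude no difference. Counts by arm are useful, but the plan attaches no rule to them. Pilot status argues for estimation, not for a no-difference claim.

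Two criticisms of the figures also have force. The 10-point yardstick is borrowed from a trigger whose scale is unstated. If the trigger is relative, the yardstick has no anchor in the document. And the result depends on convention: by a one-sided 95% limit, 10 points would be excluded more often than not at true rates of 1% or 2%. Any statement about what 64 patients can exclude must therefore name the two-sided interval. The absence of any interval or margin does not depend on either point.

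**Conclusion.** The concern holds. The plan states a no-difference hypothesis, supplies only tests of difference, sets no margin or interval criterion, and is sized on another outcome. These facts come from the text and need no assumption.

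The size of the problem does rest on assumptions: control rates of 2% to 10%, 32 analysed per arm, a 10-point rise as the yardstick, and emergency visits scored once per patient. On those terms a real rise would be missed in about 65% to 80% of trials. With equal true rates of 1% to 10%, a two-sided 95% interval would exclude such a rise in only about 20% to 26% of trials. No corresponding calculation was made for complications. The change should be made, but it does not affect the satisfaction comparison or the 64.

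**What to change.** Replace the third hypothesis with an estimation aim, and add to Data analysis:

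- The risk difference (telemedicine minus office) will be reported for emergency visits and, separately, for complications, each with a two-sided 95% confidence interval by the Newcombe or Miettinen-Nurminen method.
- A non-significant test will not be interpreted as showing no difference.
- With 64 patients, the two-sided 95% interval is unlikely to exclude a 10-percentage-point increase in emergency visits.

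If the sponsor wants to keep a positive no-difference claim, it needs a justified, prespecified margin and a sample sized for it, which step 7 suggests would exceed 32 per arm. The estimation wording costs two or three sentences and no extra patients or data. The price is a weaker safety claim.

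### An ER visit after randomisation but before the postoperative visit removes the patient and falls outside the record search, so the objective 3 emergency department comparison is made on patients selected by its own outcome

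*Combined protocol and SAP*

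**What the plan says.** All references are to the combined protocol and SAP.

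- **Allocation (Materials and Methods).** "After surgical stop-time, patients will be allocated to either a traditional postoperative visit group or a tele-medicine postoperative visit". The patient learns her arm at that point: "The envelope will contain information regarding group assignment, along with simple instructions as to how to schedule the post-operative visit". She is to "schedule the post-operative visit within a window between one and three weeks from the surgery".
- **Removal (list closing the Exclusion criteria).** The lead-in is "Recruited participants will be deemed ineligible to continue the study if", and two triggers follow. One is "After recruitment, participant experiences surgical complications (bladder or bowel injury, etc) that require face-to-face postoperative care". The other is "After recruitment, participant visits the emergency room (ER) for postoperative complaints between surgery and scheduled postoperative visit".
- **Ascertainment (Materials and Methods).** Medical records are inspected for "any phone calls to the clinic/call-center or visits to the emergency department following the postoperative encounter (within the first 30 days after surgery"). Whether the post-visit limit applies to phone calls as well as ED visits is ambiguous. The satisfaction survey is also tied to the visit: "Patients will be contacted by phone between 7 to 14 days after the postoperative visit".
- **What is to be compared (Objectives, item 3, and Hypothesis).** Surgery-related ED visits are to be compared between groups, with no difference expected. Neither section limits these to visits after the postoperative appointment. Both also mention complications, described as delayed in one and unrecognised in the other.
- **Analysis (Data analysis; Sample size).** Tests are named, but there is no analysis population, no intention-to-treat rule and no handling of removed patients. The 64 patients include no stated allowance for removals.

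**The concern.** The removal rule acts after randomisation, when the patient already knows her arm, and its trigger is one of the outcomes that objective 3 compares. The comparison is then confined to patients who reached their visit without an ER attendance, and that group is no longer protected by randomisation.

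The visit format has not yet been delivered when the rule applies. A difference between arms must therefore arise through knowledge of the allocation, which may affect care-seeking, or through visit timing, which the patient arranges within a two-week range. Both routes are open, and Strengths/limitations accepts that patients and visit providers cannot be blinded.

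At stake is the trial's statement that ED use does not differ between visit formats. Leaving early events out makes that statement less well tested. A finding of no difference could reflect the counting rule rather than the care.

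**Working it through.** **1. Order of events.** Surgery ends; the envelope discloses the arm; the removal window runs to the visit (day 7 to day 21); the ED search runs from the visit to day 30. Under the stated rules an ER visit in the removal window ends participation, and it also precedes the start of the search. Even if the removed patient's data were kept, the search as worded would not pick up that visit.

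**2. Length of the searched window**, 30 minus the visit day:

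| Visit day | Days searched | Share of 30 days |
|---|---|---|
| 7 | 23 | 77% |
| 14 | 16 | 53% |
| 21 | 9 | 30% |

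Days at risk differ between patients, and between arms if scheduling differs.

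**3. The plan's own sample size.** Inputs from the Sample size section: base score 70, 20% relative increase (14 points), SD 20, two-sided alpha 0.05, power 80%. The standardised difference is 14/20 = 0.7. The normal formula, 2 × (1.960 + 0.842)² / 0.7², gives 32.04 per arm. Rounding up gives 33 per arm (66 in total), so the stated 64 is reproduced to within two patients. With 32 per arm, t-test power is 78.7%; 33 per arm gives 79.97% and 34 per arm 81.2%.

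**4. Balanced removal and the primary outcome.** The documents give no removal rate, so 5%, 10% and 15% are assumed. The last column holds 34 analysed per arm (68 in total), the smallest whole number per arm that exceeds 80% by the t-test:

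| Removed | Analysed per arm | t-test power | Loss (points) | Randomised to keep 68 |
|---|---|---|---|---|
| 0% | 32 | 78.7% | – | 68 |
| 5% | 30.4 | 76.6% | 2.1 | 68/0.95 = 71.6 → 72 |
| 10% | 28.8 | 74.2% | 4.5 | 68/0.90 = 75.6 → 76 |
| 15% | 27.2 | 71.7% | 7.0 | 68/0.85 = 80 |

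Four of the added patients come from the step from 64 to 68, not from removals. Inflating the stated 64 for removals alone gives 68, 72 or 76.

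**5. Illustration for the ED comparison.** Counts are assumed, with 32 per arm and arbitrary direction. Let 4 v 1 patients have an ED visit before the appointment, and 2 v 2 others have one after it.

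- All randomised, counted to day 30: (4+2)/32 v (1+2)/32 = 18.8% v 9.4%, a difference of 9.4 points.
- Removed patients dropped, post-visit search only: 2/28 v 2/31 = 7.1% v 6.5%, a difference of 0.7 points.
- Removed patients kept in the denominator, post-visit search only: 2/32 v 2/32, a difference of 0.

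With balanced early visits (2 v 2), the full count gives 4/32 v 4/32 and the restricted count 2/30 v 2/30. Both differences are zero.

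**The case against.** The strongest reply is that the restricted count is a deliberate landmark analysis. Neither format has been delivered before the visit, so earlier ER visits cannot be an effect of it, and a post-visit count suits the question of what a remote visit might miss. This is a fair point, and the post-visit count should be kept. It does not make that count a measure of all surgery-related ED visits, which is how objective 3 is worded, and it does not restore comparability if disclosed allocation or scheduling influences who reaches the landmark.

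Other points stand in part:

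- The text says such patients cannot continue; it does not say outright that data already collected are discarded. The denominator is therefore uncertain, but the early visit is missed under either denominator because of the search window.
- Bladder or bowel injury may be recognised during surgery, before allocation. Only complications recognised afterwards are post-randomisation removals, and the documents do not give the split.
- The ED comparison is weak however it is done. In the illustration, Fisher's exact test gives p = 0.47 for 6/32 v 3/32 and p = 1.0 for 2/28 v 2/31, and a 4 v 1 split of early visits could itself arise by chance (p = 0.35). The illustration shows how the mechanism works; it does not predict a result.
- The halting rule in Safety Procedures might see early ER visits. It states neither a window nor a denominator, so it is undefined rather than contradictory, and a monitor's count would not repair objective 3.

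**Conclusion.** The concern holds and should be fixed. It is certain from the text that an ER visit between allocation and the appointment both ends participation and falls outside the ED search, and that no section keeps such patients in follow-up or analysis. Bias in the objective 3 comparison depends on removals or visit timing differing by arm. This is possible in an unblinded trial, but the documents support neither a size nor a direction. If both are balanced, what remains is narrower generalisability and lost power, about 2 to 7 points for the primary outcome at the assumed removal rates of 5% to 15%.

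**What to change.** Separate receiving the allocated visit format from remaining in the study. Clinical care stays as it is.

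1. Analyse every randomised patient in her allocated arm.
2. Attempt the PSQ-18 for anyone who had a postoperative visit of any format, and report the remainder as missing, by arm.
3. Count ED visits and phone calls from randomisation to day 30 for all randomised patients who have not withdrawn consent. Report the post-visit count alongside, with its days at risk, as the measure of what the visit might miss.
4. Report removals from the allocated format, with reasons, by arm.
5. Reconcile the removal criteria, the record search and the halting rule so that the window and denominator of the halting rule's ER count are stated.

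The cost is protocol wording, slightly longer chart review (day 30 is already the end point) and a few more survey calls.

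There are downsides. Some patients with complicated recoveries enter the satisfaction analysis. Calls to book the visit may add noise to the phone-call count if booking is by phone, which the documents do not say, so they are best identified separately.

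Early events also dilute a relative effect of visit format. With a constant hazard and a post-visit risk that doubles (both assumed), the full-count ratio is d/30 + 2 × (30 − d)/30 for a visit on day d: 1.77, 1.53 or 1.30 for day 7, 14 or 21, instead of 2.0. The absolute difference is unchanged; at an assumed 10% 30-day risk and a day-14 visit it is 10% × 16/30 = 5.3 points in either count. That is the reason to report both.

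### The removal rule for surgical complications has no cut-off before the envelope is opened, so patients could be removed depending on their arm

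*Combined protocol and SAP*

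**What the plan says.** The Combined protocol and SAP, Materials and Methods, sets the moment of allocation: "After surgical stop-time, patients will be allocated to either a traditional postoperative visit group or a tele-medicine postoperative visit". The ratio is 1:1, since patients are told "there is a 50% chance their post-operative visit may be via tele-medicine and 50% chance it will be as a traditional visit in the office". Allocation is made "via block-randomization, utilizing block sizes of 4:6. This will be achieved by giving patients a sealed envelope that allocates them in a sequential fashion", from a list generated in advance. The trial runs in one department and no stratification factor is named. The paragraph does not say who holds the envelopes, whether they are opaque and numbered, or whether the patient is logged before hers is opened.

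The list of reasons for becoming ineligible after recruitment, which follows the exclusion criteria, includes the case where the "participant experiences surgical complications (bladder or bowel injury, etc) that require face-to-face postoperative care". Its only timing is that the event follows recruitment.

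Strengths/limitations gives the reason for allocating late: "Randomization will occur after the surgical procedure is completed to avoid bias that could affect intra-operative technique or decisions". The same section accepts that "patients and providers who are doing the post-operative visit cannot be blinded".

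**The concern.** Recruitment precedes surgery and the envelope follows it. A complication during surgery is therefore known by the time the envelope is due. The removal rule can be applied before the envelope is opened, or afterwards with the arm in view, and the plan allows either.

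The criterion is not neutral between arms. A patient thought to need in-person care already gets it in the office arm, so nothing prompts her removal. In the telemedicine arm the same judgement clashes with the assigned visit. A conscientious clinician following the text could remove the second patient and keep the first. No misconduct is needed.

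If that happens, the telemedicine arm loses patients whose surgery went less well and the office arm keeps them. The primary outcome is a patient-reported satisfaction score in an open trial, with a hypothesis favouring telemedicine. Emergency visits and delayed complications are also compared between arms. Both comparisons would be tilted the same way.

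**Working it through.** **1. The plan's own figure.** From Sample size: base score 70, relative increase 20%, SD 20, two-sided alpha 0.05, power 80%. The difference is 0.20 × 70 = 14 points. Total N = 4 × (20 × 2.8016 / 14)² = 64.07, which agrees with the stated 64. So there are 64 allocations, nominally 32 per arm.

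**2. Order of events.** Reading the sections together:

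| Event | When | Fixed by the plan? |
|---|---|---|
| Consent and enrolment | pre-operative visit | yes |
| Intra-operative complication becomes known | by stop-time | follows from the event |
| Envelope given and opened | after stop-time | yes, but nothing need be recorded first |
| Decision to remove for a complication | any time after recruitment | no |

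The last two rows can occur in either order. If removal comes second, it is made with the arm known. If it comes first, it depends on the arm only so far as the next arm can be guessed.

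**3. How well the next arm can be guessed with a perfect tally.** The rule is to guess the arm that is behind and toss a coin at a tie. Each block is balanced, so the tally returns to zero at every block end and the guesser need not know the block sizes.

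- Block of 4: expected correct = 1/2 + 2/3 + (2/3 × 1/2 + 1/3 × 1) + 1 = 2.833; 2.833/4 = 70.8%.
- Block of 6, by full enumeration: 4.100/6 = 68.3%.
- Equal numbers of each: (2.833 + 4.100)/10 = 69.3%.
- Simulation of 64 allocations with sizes drawn at random: 69.1%, or 0.691 × 64 = 44 correct against 32 by chance.

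The plan does not say how the two sizes are mixed, but any mix lies between 68.3% and 70.8%.

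**4. How well with the information the plan describes.** Timeline expects about 4 enrolments a week. Visits take place one to three weeks after surgery. Someone who learns arms only from visits is 4 × 1 = 4 to 4 × 3 = 12 patients behind. The same guessing rule, simulated with a delay or with gaps, gives:

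| Tally | Correct guesses |
|---|---|
| complete and current | 69.1% |
| 1 arm behind | 59% |
| 2 arms behind | 55.5% |
| 4 arms behind | 51% |
| 8 arms behind | 50% |
| current, random 10% of arms missed | 60.1% |
| current, random 25% of arms missed | 56.7% |

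On the visit channel, prediction is close to chance. Only a person who sees each arm as the envelope is opened could approach 69%, and the plan does not identify one.

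**The case against.** The strongest reply is that allocation is already protected: consent precedes surgery, the envelopes are sealed and used in sequence, the list is generated in advance and the block size varies. Most of this stands. Consent before surgery limits any influence on who enrols, and the order of the envelopes is specified. What is missing is the safeguard around their use, above all a decision on eligibility recorded before opening.

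Three stronger readings are tempting, and the documents do not support them.

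- **That staff can predict about 69% of allocations.** This is a ceiling. It needs a complete and current tally, and the unblinding of visit providers does not supply one, because visits come weeks after allocation.
- **That the blocks should therefore be replaced**, for example by a list that limits imbalance to 4. With a perfect tally that list cuts correct guesses to about 56%. Two arms behind it also gives about 56%, the same as the 4 and 6 blocks. Four behind it gives about 55% against 51%, which is worse. There is no clear gain at the delays the plan implies.
- **That the bias can be put in points.** For steering by guess, expected bias = contrast × (2p − 1) × share of allocations that can be steered, where p is the proportion of correct guesses. Assume a contrast of 4 points (0.2 of the plan's SD). The result is 4 × 0.382 × 1 = 1.5 points at p = 0.691 with every guess acted on, 0.3 with a 20% share, and 4 × 0.02 × 1 = 0.08 four arms behind. The contrast and the share are assumptions, so the range describes those assumptions and not this trial.

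It can also be said that bladder and bowel injury are the only named triggers and that close finishes are infrequent at about 4 patients a week. Few patients may be affected, which limits the severity. Baseline and surgical data are collected and could reveal some imbalance. They would not reliably show a removal decided by arm, because the reason lies in a judgement.

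The separate removal rule for emergency visits normally acts after allocation. It raises post-randomisation exclusion, not concealment, and is not part of this point.

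**Conclusion.** The point holds as a gap in the timing of the removal decision. As written, a complication known at stop-time may be judged disqualifying after the envelope is opened, and the criterion conflicts with only one arm. Following the text therefore permits removal that depends on allocation, affecting both the satisfaction and the complication comparisons.

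The size of any bias cannot be derived, because the documents give no complication rate, no expected number of removals and no scores for such patients. The blocks of 4 and 6 are a secondary factor: at most about 69% correct guesses for someone with a full, current tally, and 50% to 51% for someone four or more patients behind. The verdict rests on two readings of silence, that no log precedes opening and that no cut-off applies to the removal decision. If site procedures already impose both, the protocol need only say so.

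**What to change.** Add two sentences to Materials and Methods. First: after stop-time and before any envelope is opened, staff record the patient's code, the stop-time and the decision on whether she remains eligible under the complication rule. Second: the next sequentially numbered opaque envelope is then assigned in order of stop-time, with her code written on it before opening. If REDCap, which the trial already uses, can release assignments one at a time after that entry, it can take the place of the envelopes.

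This settles eligibility for complications known at stop-time, and fixes which patient takes the next envelope, whatever anyone can guess. It does not cover complications that emerge after allocation. The block sizes and the list can stay as they are. Which complications call for in-person care is a clinical matter and is left to the investigators; the change concerns only when the decision is made and recorded.

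Cost: one short entry per patient, with no added patients or staff.
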